Data for the in-depth interviews will be collected in person or by phone. Interviews will take place in the privacy of the PI's ([name]) office and will last approximately 45-60 minutes. Participants will be able to skip any questions they are not comfortable answering.

Surveys will include sensitive questions such as questions about sexual behavior. The benefits to collecting data online include increased self-disclosure compared to interviewer-based data collection; convenience for the participant, as he can decide when to complete it; and increased safety, as he can decide when and where it is best to answer these questions. Participants will also be able to skip any questions that make them uncomfortable.

We are sensitive to how the survey experience can affect the validity of the data. All online surveys will be as brief as possible and configured for easy completion on multiple platforms (e.g., cell phone, tablet, laptop). Based on previous research, we estimate that the Step 1 online survey will take approximately 10-15 minutes, the baseline survey will take approximately 15-20 minutes, the immediate post-test survey (end of Phase 1) will take approximately 25-30 minutes, and the end of trial survey will take about 15-20 minutes. The shorter version of the end of trial survey offered to participants who are difficult to reach and out of window will take about 5 minutes. Pop-up surveys (during Phase 2) will take less than one minute to complete.

HPV vaccination status will be verified via the Illinois Comprehensive Automated Immunization Registry (I-CARE) and participants' medical chart. Vaccination status will be confirmed in I-CARE for all RCT participants both before participants begin receiving messages and at the end of the 9-month trial. Pharmacies in the state of Illinois are required to report all vaccinations to the registry,⁵⁷ thus any HPV vaccines administered to participants at a local pharmacy over the course of the 9-month trial will be documented in I-CARE.

Additionally, medical chart data will be sought from those participants who report receiving any doses of HPV vaccine from their primary care physician over the 9-month

PROTOCOL TITLE: txt2protect

trial and those doses are not found in I-CARE. The project coordinator will contact these participants at the end of the trial and ask them to complete the medical release form (see supporting documents). Upon receipt of the signed form, the project coordinator will contact the participant's primary care doctor to verify the number and timing of any HPV vaccine doses that were received during the trial. Medical chart data will only be sought for those participants who sign the medical release form.

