1.0 Objectives

Objectives and Aims

The objective of this project is to develop and pilot test a text messaging intervention to increase human papillomavirus (HPV) vaccination in young adult men who self-identify as gay, bisexual, or queer (which for the sake of brevity, will be referred to as MSM throughout this application, although some men will be sexually inexperienced).

Specific Aim 1: Develop, iteratively refine, and pre-test messages using a 5-step formative research procedure. To achieve this aim we will use a well-established formative approach for designing targeted health interventions. The procedure consists of 5 steps: 1) conduct online focus groups, an online survey, and in-depth interviews to inform message content, 2) draft initial messages based on focus group findings and pilot data, 3) refine message content and assess acceptability using content advisory teams, 4) conduct internal alpha testing to ensure software functionality, and 5) beta test the protocol. Intended users of the program (i.e., MSM aged 18-26 years old from the Chicago metro area) will be recruited to assist with this process.

Specific Aim 2: Test the feasibility, acceptability, and preliminary efficacy of the txt2protect (t2p) text messaging intervention in a pilot randomized controlled trial (RCT). To achieve this aim, 460 unvaccinated MSM (ages 18-26) who live in the Chicago metro area will be randomly assigned to the treatment (t2p) or control condition. The treatment condition will receive a culturally appropriate text messaging-based HPV vaccination intervention based on the IMB model, whereas the control condition will receive a text messaging-based sexual health intervention that includes basic facts about HPV vaccination readily accessible online. Primary outcome measures include intervention feasibility (recruitment and retention in the trial), acceptability (satisfaction with the intervention), and preliminary efficacy as determined by initiation (receipt of the first dose) and completion of the 3-dose HPV vaccine series at the end of the 9-month trial. Vaccination status will be verified by participants' medical records and the Illinois Immunization Registry.

Hypotheses

Specific Aim 2: Participants in the t2p condition (vs. control) will report greater acceptability of the intervention and will be significantly more likely to initiate and complete the 3-dose HPV vaccine series by the end of the trial.

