HPV infection.^{1,6} The HPV vaccine is given as a 3-dose series, with the 2nd and 3rd doses administered 1-2 and 6 months after the 1st dose, respectively. The Advisory Committee on Immunization Practices (ACIP) recommends *routine* HPV vaccination in 11- and 12-year-old girls and boys, and catch-up vaccination among 13-26 year-old females and 13-21 year-old males not previously vaccinated, although males aged 22-26 may also be vaccinated.¹ Although HPV vaccine is most effective in sexually naïve youth, given their high-risk status, ACIP recommends HPV vaccine for all MSM up to age 26 regardless of whether they have been sexually active, as it is unlikely they have been exposed to all HPV types covered by the vaccine.^{1,6} Nationally, HPV vaccine uptake in males lags far behind females: About 60% of adolescent females have received at least one dose of the vaccine compared to only 41.7% of males.⁷ A similar disparity holds for completion of the 3-dose series (39.7% of females vs. 21.6% of males).⁷ **Although HPV vaccine is recommended for all MSM though age 26 years, relatively few have been vaccinated.** Recent studies with national samples of gay and bisexual men aged 18-26 found that only 13-21% had initiated the series.^{8,9} Our pilot work suggests that many MSM are simply unaware of the vaccine or perceive other important barriers to getting vaccinated. **To remedy this gap, the goal of the proposed research is to develop and pilot test a text messaging intervention to increase HPV vaccination in young MSM.** This contribution is significant because it will identify new strategies for promoting HPV vaccination among a high-risk population. Beyond these more immediate outcomes, the ultimate goal of this research is to reduce morbidity, mortality, and disparities associated with HPV-related cancers among MSM. This work will also shed light on factors that affect use of other health services for young MSM that, like vaccination, typically involve interaction with the health care system (e.g., HIV testing, mental health screening and treatment).

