The screener will also assess HPV vaccination status, which will be confirmed by consulting the Illinois Immunization Registry before enrollment. Vaccinated and unvaccinated participants will take part in Step 1, but Steps 3 and 5 will be limited to unvaccinated participants. Participants will be selected using a purposive sampling strategy to ensure a sample that is diverse in age, race, ethnicity, and sexual identity. Individuals meeting inclusion criteria will be contacted by telephone to complete the enrollment process (e.g., confirm eligibility, describe the study).

Specific Aim 2

Inclusion criteria will be identical to Aim 1 except that enrollment will be limited to individuals who have not been previously vaccinated for HPV. HPV vaccination status will be assessed twice – once in the screener and again in the baseline survey – before participants are randomized and enrolled into the study. Participants' self-reported vaccination status in the screener and baseline survey will be confirmed by consulting the Illinois Immunization Registry before enrollment.

Special Populations

We will not be recruiting any special populations (e.g., adults unable to consent, individuals who are not yet adults, pregnant women, or prisoners) for this project.

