Overview. The primary goal of Aim 2 is to pilot test the intervention to establish feasibility, acceptability, and preliminary efficacy. Young MSM in the Chicago metro area will be recruited primarily online as well as from Howard Brown Health Center, and randomly assigned to the treatment or control condition. The intervention will be divided into two phases: During Phase 1 (weeks 1 through 3) participants will receive about 10 messages per day (similar to G2G). During Phase 2 (weeks 4 through 36) message frequency will decrease to monthly messages. The precise number of messages sent per day and delivery schedule may be altered based on feedback from participants in Aim 1. To give participants sufficient time to get vaccinated and because HPV vaccination is currently achieved with 3 doses administered over a 6-month period, participants will be followed for 9 months. Participants will complete assessments at baseline, immediately after Phase 1, and at the end of the 9-month trial (in order to observe all doses). Upon study completion, vaccination status will be verified by participants' medical records and the Illinois Immunization Registry, which tracks pharmacy-delivered vaccines.

Pilot RCT. Participants will be randomized 1:1 to the treatment or control condition using the REDCap (Research Electronic Data Capture) randomization module. Intervention content will be delivered in two phases over a 36-week period. During Phase 1 (weeks 1 through 3), participants will receive about 10 messages daily. During Phase 2 (weeks 4 through 36), message frequency will decrease to monthly messages. To match for attention, message frequency will be equal across the treatment and control conditions. During Phase 2, participants will receive up to three "pop-up" surveys where they will be able to inform us if/when they receive a/each dose of HPV vaccine so messages can be appropriately tailored (e.g., switch from promoting initiation to completion of the 3-dose series). Participants with a primary care provider will be instructed to contact their provider about receiving the vaccine. If their provider does not carry the vaccine, participants will be directed to seek the vaccine at a local pharmacy (e.g., Walgreens, CVS). Uninsured and underinsured participants will be directed to HBHC, a FQHC that provides care on a sliding fee scale.

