Treatment condition. Phase 1 content will be presented in 3 modules (1 per week), each reflecting a component of the IMB: Module 1 will address **information** about HPV infection and the HPV vaccine. It will also include a "doctor's blog" to capture the important influence providers have in promoting HPV vaccination and to further legitimize the information. Module 2 will address **motivations** to receive HPV vaccine. Content will address attitudes and social norms about HPV vaccination, vulnerability to HPV infection, and vaccination intentions. Module 3 will focus on **behavioral skills** and self-efficacy for initiating and completing the 3-dose series such as scheduling an appointment, talking with their doctor about the vaccine (and possibly their sexual identity), verifying whether their health insurance covers the vaccine, and finding

PROTOCOL TITLE: txt2protect

alternative locations to receive the vaccine (such as a pharmacy) if it is not carried by their physician. Each module will include tips that address potential barriers relevant to each IMB component. Phase 2 “booster” messages will largely reinforce Phase 1 content to foster continued engagement with the program, although some new content will also be introduced. For example, messages will shift to encourage vaccine completion when a participant initiates the series.

Control condition. Phase 1 content will be presented in 3 modules; however, unlike the treatment group, content will be topic-based rather than theory-based and will focus on general sexual health. Module 1 will address basic facts about HIV and STIs, including HPV. Module 2 will address HIV/STI prevention (e.g., condom use) and will include basic facts about HPV vaccination that are currently available online. Module 3 will address healthy relationships. Phase 2 messages will reinforce Phase 1 content to maintain engagement.

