11.0 Data and Specimen Management

Analysis Strategy

Intervention feasibility will be computed as outlined above and summarized in a CONSORT map. Acceptability of the intervention will be assessed with descriptive statistics for the closed-ended items and with the same qualitative approach used for the online FG data for the open-ended items. Intervention efficacy will be assessed using an intent-to-treat approach. T-tests and chi-square analyses will be used to compare baseline characteristics of participants in the treatment vs. control condition. Separate chi-square analyses will be conducted for HPV vaccine initiation (receipt of ≥ 1 dose) and completion (receipt of 3 doses) to assess effects of treatment. Secondary analyses will examine potential differences in IMB constructs at the end of Phase 1 by treatment arm and assess whether they mediate effects of t2p on vaccine uptake. Following [name],³⁴ we will also conduct a detailed analysis of barriers to vaccine uptake among participants who did not get vaccinated over the course of the study to inform additional modifications for the large-scale trial.

Power Analysis

Based on previous studies,^{14, 41, 43, 54} we hypothesize that 18-21% of treatment arm participants will receive their 1st dose of HPV vaccine, compared to 6-8% of control arm participants. The comparison of outcomes between arms, with two-sided alpha = 0.05, will have $> 80\%$ power for all scenarios with N=192 per condition. Based on previous

PROTOCOL TITLE: txt2protect

studies with similar samples (G2G, Keep It Up! [KIU!])^{38, 49} and retention rates as high as 85-95% with follow-ups as long as one year, we anticipate an attrition rate of 5-20%. Using the most conservative estimate (20%) we will enroll 230 participants per arm to account for attrition.

Steps to Maintain Data Security and Confidentiality

Participant privacy and data will be carefully protected. Online surveys will be conducted online using a secure web-based application (REDCap).

To maintain privacy in the online focus groups, all participants will be asked to use pseudonyms rather than their real names, and to refrain from mentioning others by name. This will help to ensure openness. If any personal information is inadvertently disclosed, names or other identifying information will be redacted from the focus group transcripts.

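### Nine months of follow-up can show three on-schedule doses only for men who start by about month 3, so the completion result should be read as three doses by month 9 and not as evidence on finishing the series

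*Combined protocol and SAP*

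**What the plan says.** Section 1.0 (Specific Aim 2) lists, beside initiation, "completion of the 3-dose HPV vaccine series at the end of the 9-month trial" as a measure of preliminary efficacy. Section 3.0 states for Aim 2 that "enrollment will be limited to individuals who have not been previously vaccinated for HPV", so all three doses must fall inside the trial. Section 2.0 describes a three-dose series "with the 2nd and 3rd doses administered 1-2 and 6 months after the 1st dose, respectively".

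Section 9.0 (Research Design for Aim 2, Overview) gives two reasons for the length of follow-up: time to get vaccinated, and a series of "3 doses administered over a 6-month period, participants will be followed for 9 months". It places the final assessment "and at the end of the 9-month trial (in order to observe all doses").

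Messaging lasts as long as the trial: "Intervention content will be delivered in two phases over a 36-week period". In the treatment arm, "messages will shift to encourage vaccine completion when a participant initiates the series", and pop-up surveys in Phase 2 tell the team when to make that switch. Starts during Phase 2 are therefore expected.

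Section 11.0 (Analysis Strategy) uses an intent-to-treat approach. "Separate chi-square analyses will be conducted for HPV vaccine initiation" (at least one dose) and for completion (three doses). The plan has no category for a series still on schedule at closing, no time-to-dose analysis and no registry check after the end of the trial.

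**The concern.** The stated purpose of the month-9 assessment is a property that the design has only for early starters. Take two men who each follow the schedule exactly. One starts in month 2 and is a completer at month 9. The other starts in month 4, is due his third dose in month 10, and is a non-completer. On that outcome he is grouped with men who abandoned the series and men who never started.

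What is at stake is interpretation. A higher completion rate under t2p could come from more starts, earlier starts, better continuation, or any mixture. A low rate in either arm would look like poor follow-through when part of it is only that the series had no time to finish.

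**Working it through.** **Inputs from the documents.** Third dose 6 months after the first (section 2.0). Follow-up 9 months and messaging 36 weeks (section 9.0). First-dose rates of 18-21% under treatment and 6-8% under control, two-sided alpha 0.05, 192 per arm (section 11.0, Power Analysis).

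**The plan's own figure.** Section 11.0 claims more than 80% power, and its assumed rates are for the first dose only. With p̄ the mean of p1 and p2, power = Φ{[|p1 − p2|√n − 1.96√(2p̄(1 − p̄))] / √(p1(1 − p1) + p2(1 − p2))}. For the least favourable pair, 18% versus 8% with n = 192:

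[0.10 × 13.856 − 1.96 × √0.2262] / √0.2212 = (1.3856 − 0.9322) / 0.4703 = 0.964, and Φ(0.964) = 83%.

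The claim reproduces. No figure is given for completion.

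**Latest useful start.** Follow-up minus series length = 9 − 6 = month 3. If closing is taken at week 36, it is 36 − 26 = week 10, about month 2.3.

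**Ceiling on completion.** Ceiling = initiation rate × share of starters who begin by month 3, with no dose missed. The documents give no start times, so the share is an assumption. Uniform starts over 9 months give 3/9 = 33%. Exponential start times (truncated at 9 months) with medians from 4.5 down to 1 month give 49% to 88%.

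| Share starting by month 3 | Treatment ceiling (from 18-21%) | Control ceiling (from 6-8%) |
|---|---|---|
| 33% | 6.0-7.0% | 2.0-2.7% |
| 50% | 9.0-10.5% | 3.0-4.0% |
| 70% | 12.6-14.7% | 4.2-5.6% |

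**Power at these ceilings.** Assume the same share in both arms and 192 per arm. The formula above gives 36%, 51% and 67% for 18% versus 8% initiation, and 66%, 84% and 94% for 21% versus 6%. The section 11.0 figure does not carry over to completion.

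**Timing alone (illustration with assumed figures).** Let 20% start in each arm and nobody miss a dose. If 70% of starters in one arm and 33% in the other begin by month 3, completion is 0.20 × 0.70 = 14.0% versus 0.20 × 0.333 = 6.7%. Follow-through is identical in the two arms.

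**An up-to-date outcome does not cure this.** A tempting alternative counts a man as a success if he has started and no dose is overdue at month 9. The second dose is due by 2 months, so anyone starting after 9 − 2 = month 7 passes automatically. Assume 20% start in each arm and 70% take each dose as it falls due. The chance of being up to date is then 0.7 × 0.7 = 0.49 for starts by month 3, 0.70 for months 3-7, and 1 for months 7-9.

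- Arm A, 70% by month 3 and the rest uniform over months 3-9: 0.70 × 0.49 + 0.30 × (4/6 × 0.70 + 2/6 × 1) = 0.583, and × 20% = 11.7%.
- Arm B, uniform over 9 months: 3/9 × 0.49 + 4/9 × 0.70 + 2/9 × 1 = 0.697, and × 20% = 13.9%.

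The later-starting arm looks better with the same adherence.

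**The case against.** The strongest reply is that the outcome is explicitly bounded in time. Section 1.0 defines completion at the end of the trial and states its hypothesis the same way. If t2p brings starts forward and more men hold three doses at month 9, that is a real effect on the stated outcome. This stands: a reader might infer that the completion test is biased or invalid, and the documents do not support that.

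The window was also deliberate. Section 9.0 justifies 9 months by time to start plus a 6-month series, which leaves 3 months of slack. That is reasonable for early starters, but it does not make the remark about observing all doses true for the others.

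A reader might infer that late starts earn no credit. They do: initiation is tested separately and is the outcome whose rates the power analysis uses.

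A reader might also infer that the completion test mainly measures who started early. That cannot be shown. Messaging is front-loaded, at about 10 a day for 3 weeks and then monthly, so many starts may be early and the 33% case may be pessimistic. Message frequency is equal across arms, and a share common to both arms leaves the ratio of the ceilings unchanged.

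Finally, section 11.0 links the large-scale trial only to the analysis of barriers among men who were not vaccinated. It does not say that the completion rate will feed into that trial.

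**Conclusion.** The point holds as one of wording and interpretation, and it is worth correcting. The month-3 limit follows directly from the protocol's own schedule and follow-up. That later starters count as non-completers follows from a chi-square on three doses under intent-to-treat, although the plan does not say so in words. The comparison remains valid for three doses by month 9, and initiation is unaffected. Completion alone cannot support a statement that t2p helps men finish the series, and the raw rate understates follow-through to the extent that men start after month 3.

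That extent is unknown. Over the shares of 33% to 70% shown above, the treatment ceiling runs from 6.0% to 14.7%, assuming the planned initiation rates and no missed dose.

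**What to change.** 1. In section 9.0, replace the remark about observing all doses with a statement that three on-schedule doses can be observed only for men who start by about month 3.
2. In section 11.0, keep the chi-square, name the outcome three doses by month 9, and limit its conclusion to that.
3. Pre-specify a descriptive table, by arm and in all randomised men, with four categories at closing: no dose; started with a dose overdue on the section 2.0 schedule; started with the series in progress and nothing overdue; three doses. Beside it, report the number who started by month 3 and three-dose completion among them. Do not test these figures, because starting is a post-randomisation event.
4. Do not base conclusions about continuation on up-to-date status at month 9, because it favours late starts.
5. Confirm that dose dates are extracted from I-CARE. The documents mention dose timing only for chart verification, which needs a signed release and a physician dose missing from the registry, and for the pop-up surveys (both section 9.0). The month-9 questions described in section 8.0 cover number and place of doses.

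The cost is a few sentences and one more descriptive table, with no added participants or contacts. Dates will be incomplete for some men, and the table should show how many.

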To complement the online FGs, we will also conduct an online survey and in-depth interviews. Our pilot data for this project focused on a national sample of YMSM. As the current project specifically targets YMSM in the Chicago area, we would like to gain a better understanding of facilitators and barriers to HPV vaccination for our local population. Although these factors will be assessed in the online focus groups, we believe that these additional data collection formats will allow for a richer understanding of men's knowledge, attitudes, and beliefs regarding HPV vaccination than could be supplied in a focus group alone. See Appendix 8 and 9 for the online survey and interview guide.

Step 2: Draft initial messages. Transcripts from the FGs will be imported into Dedoose,⁵¹ a mixed-methods analysis program. Two rounds of constant comparison analysis will be conducted to create and refine the codebook, which will be followed by a thematic content analysis.^{52, 53} Using these themes in conjunction with results from our pilot work,⁸ [name] will draft an initial pool of messages. Treatment condition messages will be written to directly address IMB components, with special emphasis on barriers relevant to each component. Messages will take into account unique socio-cultural and developmental factors relevant to gay, bisexual, and queer men to ensure that content is appealing and culturally appropriate. Control condition messages will include basic facts about HPV vaccination currently available online plus general sexual health content adapted from G2G. Control messages will be largely informational yet, to ensure a blinded control group, will be aligned with what young MSM might expect in a sexual health program. Messages will be reviewed by Drs. [name], [name], and [name] and subjected to further edits and review, as necessary.

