Participants who are difficult to reach and are out of window for completing their Phase 2 survey will be offered the option to complete a shorter version of the survey. This survey will take approximately 5 minutes to complete and have an emphasis on the primary outcomes of the study. This will be a last resort option, as we want most participants to complete the full Phase 2 survey. Participants will also have the option to complete this shorter survey online on their own or over the phone with the Project Coordinator. Participants who complete the shorter version of the Phase 2 survey will be

PROTOCOL TITLE: txt2protect

paid \$20 instead of the standard \$45 received by participants who complete the full Phase 2 survey.

During Phase 2, participants may also receive up to three “pop-up” surveys, depending on their vaccination status at the end of Phase 1. Participants who complete a pop-up survey within the designated time frame will be eligible for a monthly \$50 e-raffle. Surveys will be brief and configured for easy completion on multiple platforms (cell phone, tablet). Participants will receive special data collection text messages with the link to each survey. Participants who do not respond will receive up to 3 reminders by text and email. See Appendix 5 for draft surveys for the pilot RCT.

Sources of Materials

Participants enrolled in Steps 1 and 3 will take part in an online focus group. Some participants enrolled in Step 1 will take part in an online survey or an in-depth interview. Participants enrolled in Step 3 (CATs) will also complete a survey to provide feedback on the initial messages. Participants enrolled in Step 5 (beta test) will complete assessments at baseline and immediate post-test (3 week follow-up). Participants enrolled in the pilot RCT will complete assessments at baseline, immediately after Phase 1, and at the end of the 9-month trial. RCT participants may also receive up to three “pop-up” surveys during Phase 2.

Data for the focus groups will be collected using a secure online message board that members of our team have used successfully in previous research. All survey data will be collected online through REDCap, a secure, web-based application designed to support data capture for research studies.

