For the beta test and pilot RCT, participants deemed to be eligible (based on their screening survey responses) will be sent a text message welcoming them into the study. The text message will also contain a link to the consent form, which will be followed by the baseline survey. The project coordinator will direct and oversee the consent and enrollment process. Before participants are randomized, the project coordinator will confirm that participants have received no doses of HPV vaccine since screening by checking their self-reported vaccination status in the baseline survey as well as the I-CARE registry.

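### No masking to arm is specified for the coordinator who takes phone outcome surveys and pursues chart proof of doses, and effort on the chart step is not fixed

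*Combined protocol and SAP*

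**What the plan says.** Section 9.0 (Assessments), repeated in section 22.0, offers a short Phase 2 survey to men who are hard to reach and out of window. It concentrates on the primary outcomes and is described as a last resort. Men may "complete this shorter survey online on their own or over the phone with the Project Coordinator".

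Section 9.0 (Sources of Materials) and section 25.0 set out how doses are verified. I-CARE is checked for all RCT participants before messages start and at the end of the trial. If a man reports a dose from his primary care physician and it is not in I-CARE, a chart is sought: "The project coordinator will contact these participants at the end of the trial", asks for a signed release and, once it is received, contacts the physician. Without a signature no chart is sought.

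The one statement on masking concerns participants. In section 9.0, Step 2, control messages are written "to ensure a blinded control group". The text does not say whether anyone who collects or verifies outcomes can see the allocation.

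**The concern.** Vaccine initiation and completion are compared between arms, so doses must be found with equal effort in each. For pharmacy doses this is largely secured, because section 8.0 says pharmacies must report to the registry and the registry is searched for everyone. For physician doses the documents state no such reporting duty. Section 9.0 nevertheless sends men who have a provider to that provider first, and to a pharmacy only if the provider does not carry the vaccine. The chart step thus backs up the first-line route.

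How hard someone tries on that step is left open. The limit of three reminders in section 9.0 concerns survey links, not release requests or calls to physicians. If the person doing this work knows the arm and is more persistent in t2p, more t2p doses become verified and the difference is biased upward. In phone mode the same person may also elicit the self-report that triggers the chart request. Section 11.0 plans no reporting by survey mode or by source of verification, so unequal capture would not show in the results.

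**Working it through.** **The plan's own figure.** Section 11.0 gives "two-sided alpha = 0.05", "18-21% of treatment arm participants will receive their 1st dose of HPV vaccine, compared to 6-8% of control arm participants", and more than 80% "power for all scenarios with N=192 per condition". With pooled variance under the null, power = Φ{[|p1 − p2|√n − 1.96√(2p̄(1 − p̄))] / √[p1(1 − p1) + p2(1 − p2)]}. At n = 192:

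| t2p vs control | Power |
|---|---|
| 18% vs 6% | 95.4% |
| 18% vs 8% | 83.3% |
| 21% vs 6% | 99.2% |
| 21% vs 8% | 95.4% |

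The statement is reproduced. These figures take the observed rates to be the true ones.

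**Inputs for unequal capture.** The plan gives none, so these are assumptions, apart from n and the 8%, which is the upper end of the plan's control range:
- true initiation is 8% in both arms, so there is no effect;
- 40% of doses can be proved only by chart, and the other 60% are found in I-CARE in both arms;
- chart recovery is 80% in t2p and 40% in control;
- a dose that is not verified is not counted;
- n = 192 per arm.

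**Observed rates.** Observed = true rate × (0.6 + 0.4 × recovery).
- t2p: 8% × (0.6 + 0.4 × 0.8) = 8% × 0.92 = 7.36%, or 192 × 0.0736 ≈ 14 men.
- Control: 8% × (0.6 + 0.4 × 0.4) = 8% × 0.76 = 6.08%, or 192 × 0.0608 ≈ 12 men.
- Spurious difference: 7.36 − 6.08 = 1.28 percentage points.

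**False-positive rate.** I summed the binomial probabilities of every pair of counts for which the uncorrected chi-square test rejects at two-sided 0.05. With 8% in both arms the rate is 5.0%. With 7.36% vs 6.08% it is 7.9%.

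**Range.** Here t2p capture is complete, and control alone loses part of the doses that depend on the coordinator. Control observed = true rate × (1 − share × loss).

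| True rate | Share of doses dependent | Lost in control | Control observed | False-positive rate |
|---|---|---|---|---|
| 8% | 10% | 25% | 7.8% | 5.1% |
| 8% | 20% | 50% | 7.2% | 6.1% |
| 8% | 40% | 50% | 6.4% | 9.3% |
| 18% | 10% | 25% | 17.55% | 5.2% |
| 18% | 20% | 50% | 16.2% | 7.6% |

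**Scale against the hypothesised effect.** The plan's differences run from 18 − 8 = 10 to 21 − 6 = 15 points. The 1.28-point artefact is about an eighth of the smallest (1.28 / 10 = 0.128).

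**The case against.** The strongest reply is that the plan is silent on masking, which is not the same as being unmasked. Randomisation and messages both run in REDCap, and the coordinator may never see the allocation. That stands: a reader might infer that this person is known to be unmasked, and the documents do not support it.

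Three other inferences also fail.
- **That the coordinator chooses whom to pursue.** Sections 8.0, 9.0 and 25.0 give one trigger with no arm element, and the man's signature is also needed. Only persistence is discretionary.
- **That the enrolment role is part of the problem.** Section 28.0 says "The project coordinator will direct and oversee the consent and enrollment process", but the eligibility check there precedes randomisation and reveals no arm.
- **That phone ratings inflate acceptability, so those items should leave the call.** The short survey's items are not shown; that it contains the satisfaction scale is inferred from its focus on primary outcomes. The Phase 1 measure has no phone option. Any upward drift would be an effect of survey mode that masking would not remove. The plan's remark that online collection brings "increased self-disclosure compared to interviewer-based data collection" follows a sentence about sexual behaviour and says nothing of satisfaction or vaccination.

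It is also fair that I-CARE is searched for everyone, that phone is optional within a last-resort survey, and that the sizes above rest on assumed inputs. The upward bias further requires that unverified self-reports are not counted, and the plan states no counting rule. These points limit the concern. They do not supply a stated safeguard for the chart and phone steps.

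**Conclusion.** The point holds in a limited form. No masking is specified for the role that may take the short survey by phone and that obtains releases and charts, and no attempt limit makes the chart effort equal. What is exposed is capture of physician doses missing from I-CARE, and answers given by phone.

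The likely size is modest. With recovery twice as high in t2p and 40% of doses provable only by chart, the false-positive rate rises from 5.0% to about 7.9%. If 10–20% of doses depend on the coordinator and 25–50% of those are lost in control only, it is 5.1–6.1% at a true rate of 8%. Neither range comes from trial data. This would not by itself produce an effect of the size the plan hypothesises. It is still worth closing, because section 11.0 looks ahead to a large-scale trial and the safeguard is cheap.

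**What to change.** 1. State who can see the allocation. Work the month-9 I-CARE look-ups, phone short surveys, release requests and chart requests from an ID list without arm. Where existing staffing allows, hide the REDCap allocation field from whoever does this work.
2. Use the same scripted wording and the same fixed maximum number of contact attempts in both arms, for the participant and for the physician's office.
3. Record survey mode (online or phone) and verification source (I-CARE, chart, self-report only) for each man, and report both by arm.
4. Add a sensitivity analysis of initiation and completion that counts I-CARE doses only. It takes the chart step out of the comparison, at the price of missing physician doses that were never registered.

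The cost is a permission setting, a short script, an attempt count, two recorded fields and one extra analysis. A few doses may stay unverified once the attempt limit is reached. Accidental unmasking, for example when a man describes his messages during a call, should be logged.
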